## **3. STUDY DESIGN**

This is a multi-center, observational study involving retrospective collection of NSCLC patients information. All consecutive patients who had a newly diagnosis of NSCLC in 2017 from healthcare administrative database and received at least one anti-cancer drug treatment between January 2017 and December 2017, identified through the proposed algorithm, will be considered. All data needed for KPI calculation, even if they fall outside January-December 2017 period, will be collected. The end of data collection will be defined as patient death or 30 June 2018, whichever came first.

A set of potential KPIs had been developed from a panel of experts (clinicians, IT experts etc..) to investigate the appropriateness of activities within NSCLC care pathway, with a special focus on the use of immunotherapy.

The eligible population and data will be gathered retrospectively through an algorithm from administrative databases (SDO, REM, ASA, FED, AFT, ADI, SDHS-hospice).

Administrative data will be used as unique resource:

- to identify patients cohort;
- to measure KPIs along care pathway ;

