### 5.1 Clinical variables of interest for the study

The only source for clinical information will be administrative databases in all its parts.

[figure not shown]
We will focus primarily on the following set of clinical data:

- Biopsy at diagnosis;
- Presence of metastatic NSCLC at diagnosis;
- Neoadjuvant treatment before lung cancer surgical resection;
- Lung cancer main surgical resection;
- Length of stay in hospital after lung major surgery;
- Main information regarding anti-cancer drug treatments at the first diagnosis and for subsequent lines
- Multidisciplinary team (MDT) meeting discussion;
- Radiotherapy (RT) in the end of life;
- Death;
- Integrated home care utilization;
- Hospice care utilization.

[figure not shown]

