34.6	SCARIFICATION OF PLEURA														
4	
Percentage of surgical patients on the total number of patients with exploratory thoracotomy in inpatient setting.            NUM: Total of patients with only exploratory thoracotomy procedure (Cod 34.02);            DEN: Number of surgical patients;            For major surgery, ICD-9-CM codes were selected as reported for KPI 3.            Surgical patients defined as patients who receive any surgical procedure (major and/or explorative)
														
5	
Percentage of patients undergoing neoadjuvant therapy ( CT or CT+RT within 6 months prior to the first major resection date)            NUM: Number of patients who underwent induction treatment as CT or CT+RT in the 6 months prior to surgery;            DEN: Total number of surgical patients;            The algorithm will not be able to identify patients who received neoadjuvant therapy in clinical trials.            For major surgery, ICD-9-CM codes were selected as reported for KPI 3.
														
6	
30-day mortality rate from major surgery            NUM : Number of patients who died within 30 days from major surgery;            DEN: Total number of surgical patients;            For major surgery, ICD-9-CM codes were selected as reported for KPI 3.
														
7	
Percentage of patients discussed in the multidisciplinary team (MDT) meeting at least once in the year of incidence            NUM: Number of patients discussed at least one time in MDT meetings;            DEN: Total number of patients identified by the algorithm;
														
8	
Percentage of patients who performed imaging exams such as MRI, TC and PET within 7 days from MDT meeting            NUM: Number of patients who performed imaging exams within 7 days from MDT meeting;            DEN : Total number of patients discussed in MDT meeting;
														
9	
Average and range of length of stay calculated as the mean difference among date of discharge and date of admission.
														
10	
Average time between biopsy and the first administration of systematic anti-cancer drug (excluded neoadjuvant patients of KPI 5) calculated as the average difference among biopsy and the first date of administration of chemotherapy.            For patients enrolled in experimental clinical trial will not be possible to retrieve information on therapies from administrative database.
														

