11	
KPIs on THERAPIES For patients enrolled in experimental clinical trial will not be possible to retrieve information on therapies from administrative database.
 
a) Percentage of patients treated with immunotherapies NUM: Patients with at least one administration of immunotherapy According to Anatomical Therapeutic Chemical Classification System ATC, the following codes will be investigated: L01XC17 nivolumab L01XC18 pembrolizumab L01XC32 atezolizumab
 
DEN: Total number of patients identified by the algorithm who underwent anti-cancer drug treatment for NSCLC, as single or double agent chemotherapy, target therapy etc..(excluded neoadjuvant patients of KPI 5)
 
b) Percentage of patients who underwent immunotherapy for more than 6 months after first dose. NUM: Number of patients who underwent immunotherapy more than 6 months after the first administration; DEN: Total number of patients identified by the algorithm who underwent immunotherapy;

12	
Percentage of patients who underwent anti-cancer drug treatment in the last 30 days of life NUM: Number of patients who underwent anti-cancer drug treatment in the last 30 days of life; DEN: Total number of patients identified by the algorithm who deceased

13	
Percentage of patients who underwent the first administration of systematic anti-cancer drug within 30 days from discussed in MDT meeting NUM: Number of patients who underwent first systematic anti-cancer drug administration within 30 days from MDT; DEN: Total number of patients patients identified by the algorithm discussed in MDT meeting;

14	
Percentage of patients who underwent RT in the last 30 days of life ( excluded palliative treatments single fraction) NUM: Number of patients who performed RT in the last 30 days of life ( excluded palliative treatments); DEN: Total number of patients identified by the algorithm who deceased;

15	
Percentage of patients who underwent at least one Integrated Home Care (IHC) NUM: Number of patients who underwent IHC service; DEN: Total number of patients identified by the algorithm;

16	
Percentage of patients who underwent at least one hospice care NUM: Number of patients who underwent hospice care; DEN: Total number of patients identified by the algorithm;

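### KPI 10 ends its interval at the first anti-cancer drug in its title but at the first chemotherapy in its calculation line; KPI 14 likewise words one exclusion in two ways

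*Protocol*

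**What the plan says.** KPI 10 in protocol section 5.2 is titled "Average time between biopsy and the first administration of systematic anti-cancer drug". Its calculation is then given as "calculated as the average difference among biopsy and the first date of administration of chemotherapy". It leaves out the neoadjuvant patients of KPI 5, and it notes that the therapies of patients in experimental trials cannot be retrieved. There are no separate numerator and denominator lines, so the calculation clause is the only instruction for computing it.

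The denominator of KPI 11a describes anti-cancer drug treatment "as single or double agent chemotherapy, target therapy etc..(excluded neoadjuvant patients of KPI 5". Its numerator picks out immunotherapy by three ATC codes.

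The wider term is used elsewhere:
- Section 3, cohort entry: "received at least one anti-cancer drug treatment between January 2017 and December 2017".
- Section 5.1, variables: "Main information regarding anti-cancer drug treatments at the first diagnosis and for subsequent lines".
- KPI 12, numerator: "Number of patients who underwent anti-cancer drug treatment in the last 30 days of life".
- KPI 13, numerator: "Number of patients who underwent first systematic anti-cancer drug administration within 30 days from MDT".

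In KPI 14 (radiotherapy in the last 30 days of life), the title confines the exclusion to single-fraction palliative treatment. The numerator excludes palliative treatment with no mention of fractions.

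**The concern.** KPI 10 has two end points, and they give the same date only for a patient whose first drug is chemotherapy. A programmer would normally code from the calculation clause. A patient who starts on immunotherapy or a targeted drug would then have no end date, or would be given the date of a later chemotherapy line. KPI 10 serves the primary objective, and the indicator set has a declared focus on immunotherapy, so the patients affected are among those of most interest. The primary objective also looks at care across three sites. If the sites differ in first-line drug mix, the literal reading could produce a difference in waiting time that comes from the coding. The chart review at IRST would not correct this, since charts are consulted only to validate case identification.

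**Working it through.** **Are the two terms interchangeable in this protocol?** KPI 11a is the percentage treated with immunotherapy among those given anti-cancer drug treatment. For that to be a proportion, immunotherapy must lie inside anti-cancer drug treatment. The same denominator lists chemotherapy and target therapy side by side as examples. Chemotherapy is therefore a subset of the wider term.

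**Which line is the outlier?**

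| Place | Term used |
|---|---|
| KPI 10 title | anti-cancer drug |
| KPI 10 calculation | chemotherapy |
| KPI 12 numerator | anti-cancer drug |
| KPI 13 title and numerator | anti-cancer drug |
| Sections 3 and 5.1 | anti-cancer drug |

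Only the KPI 10 calculation line narrows the event. KPI 13 uses the same first-drug event as KPI 10's title.

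**What the literal reading would do.** The protocol states no figure for KPI 10, so there is nothing to reproduce. The following shows direction and mechanism only; every input except the calendar dates is an assumption.

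- f = share starting on a non-chemotherapy drug: 15%, 25%, 35%.
- q = share of these who later receive chemotherapy: 0 or 30%.
- D = days from biopsy to that chemotherapy: 120 or 180.
- True interval: 45 days for everyone.

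Follow-up: section 3 requires a drug by 31 December 2017, so with a 45-day interval the latest biopsy is 16 November 2017. Adding 180 days gives 15 May 2018. Section 3 also says "The end of data collection will be defined as patient death or 30 June 2018, whichever came first", so for survivors both values of D are fully observed.

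Dropped share = f(1 − q). Literal mean = [(1 − f)·45 + f·q·D] / [(1 − f) + f·q]. Mis-dated share of those counted = f·q / [(1 − f) + f·q].

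With f = 0.25, q = 0.30, D = 180:
- dropped: 0.25 × 0.70 = 17.5%
- mean: (33.75 + 13.5) / 0.825 = 57.3 days
- mis-dated: 0.075 / 0.825 = 9.1%

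| f (q = 0.30) | Dropped | Mean, D = 120 | Mean, D = 180 | Mis-dated among counted | Median |
|---|---|---|---|---|---|
| 15% | 10.5% | 48.8 | 51.8 | 5.0% | 45 |
| 25% | 17.5% | 51.8 | 57.3 | 9.1% | 45 |
| 35% | 24.5% | 55.4 | 63.8 | 13.9% | 45 |

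With q = 0 the dropped share is f itself (15% to 35%) and the mean stays at 45. In the other cells the maximum moves from 45 to D and the SD rises with it. The median does not move, because the mis-dated patients are far fewer than half of those counted. With real variation in waiting times the median could shift somewhat, and the mean could move even with q = 0 if the dropped patients' true waits differ from the rest.

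**KPI 14.** The title and numerator differ for one group: decedents whose radiotherapy in the last 30 days was all palliative and included a multi-fraction course. They count under the title and not under the numerator. The protocol gives no deaths, radiotherapy counts or fractionation data, so the gap cannot be sized.

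**The case against.** The strongest reply is that the protocol points to one reading. The title, KPIs 12 and 13, and sections 3 and 5.1 all use the wider term, so the calculation line may simply use chemotherapy loosely. If so, only the wording is wrong and no result changes. That is plausible and stands as a limit on the point. It does not remove it, because the next row separates the terms and nothing says which line governs. Nor is this a detail that can be left to an analysis plan: the protocol has already fixed two definitions, and a plan cannot follow both.

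A second reply is that the study is descriptive, calls its indicators potential ones, tests no hypothesis, and reports the median beside the mean (section 7.3). That also stands, and it limits the consequence.

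A reader might go further and infer that KPI 10 will be biased by a known number of days or patients. The documents do not support this: they give neither first-line drug mix nor waiting times, and the literal coding is a possibility, not a stated intention. A reader might also infer that following the title makes KPI 10 free of bias. KPI 10's own note rules that out, since trial patients' therapies stay out of reach on either reading. Section 5 has a sentence limiting the data to 2017, but its conflict with section 3 is a separate matter and is not used here.

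For KPI 14, other numerators (KPIs 3 and 7) shorten their titles, so the missing limit may be shorthand. Here, however, the missing words decide who is counted.

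**Conclusion.** The mismatch in KPI 10 is certain on the text; its effect depends on how the line is coded. As written, the calculation line contradicts its own title. Followed literally, it drops patients who start on immunotherapy or a targeted drug, or dates them at a later chemotherapy line. The population counted would change, the mean could lengthen, the SD and maximum could widen, and the median may change little. The size cannot be derived from the protocol, and the illustrative means and shares rest on assumed inputs. The KPI 14 discrepancy is real but secondary, with no size claimed. Both should be corrected before extraction.

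**What to change.** In the KPI 10 calculation line, replace the word chemotherapy with: any systemic anti-cancer drug (chemotherapy, targeted therapy or immunotherapy). This matches the title and KPI 13. It costs one phrase and uses drug dates already needed for KPIs 11 to 13. Keep the existing note on trial patients, since the change does not resolve that gap.

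In KPI 14, reconcile the title and numerator to one identically worded exclusion before data are extracted, after checking that the administrative radiotherapy records can identify whatever is chosen. The cost is one phrase and that check.

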### **7.3 Data analysis**

For primary objective, for each indicator, the proportion of patients who receive the procedure, in the defined time window, among those eligible will be calculated. Descriptive statistics as arithmetic mean and standard deviation (SD) as well as median value and minimum–maximum statistics will be presented for KPI related to average time. Two-sided 95% confidence interval (95% CI) will be reported as appropriate and specified for KPI expressed as proportion. For secondary objective, the validity of algorithm will be evaluated by individual matching among cases retrieved from administrative database and medical chart obtained from IRST. Following definition will be used to explain this objective: NSCLC cases appearing as incident cases in administrative database, but not in IRST clinical chart will be considered as false positive and those appearing in IRST clinical chart but not in administrative database will be considered as false negatives.

Sensitivity will be defined as the percentage of NSCLC cases correctly identified by the algorithm and calculated as the proportion among NSCLC cases identified both in administrative database and IRST clinical chart ('true positive' cases) and all cases identified as NSCLC cases from IRST clinical chart ('true positive' + 'false negative' cases). Positive predictive value will be defined as the percentage of NSCLC patients identified from IRST clinical chart were really NSCLC. This proportion will be calculated as the proportion among NSCLC cases identified both in administrative database and IRST clinical chart ('true positive' cases) and all cases identified as NSCLC cases from administrative database ('true positive' + 'false positive' cases).

Likewise, specificity and negative predictive value will be calculated, and exact (Clopper-Pearson) 95% confidence limits for binomial distribution will be applied.

Statistical analysis will be performed using Stata software 15.1/SE for Windows (Stata Corp LP, USA).

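### KPI 11b requires more than 6 months of observation after the first immunotherapy dose but has no follow-up limit in its denominator, so patients starting from 30 December 2017 always count as not continuing

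*Protocol*

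**What the plan says.** Section 5.2 titles KPI 11b "Percentage of patients who underwent immunotherapy for more than 6 months after first dose". Its numerator and denominator are given as "NUM: Number of patients who underwent immunotherapy more than 6 months after the first administration; DEN: Total number of patients identified by the algorithm who" received immunotherapy. No latest start date and no minimum follow-up is attached.

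Section 3 sets the data window: "The end of data collection will be defined as patient death or 30 June 2018, whichever came first". For cohort entry it asks for a new diagnosis in 2017 and that the patient "received at least one anti-cancer drug treatment between January 2017 and December 2017"; the drug need not be immunotherapy. It adds: "All data needed for KPI calculation, even if they fall outside January-December 2017 period, will be collected". Section 5.1 lists treatment in later lines among the variables collected.

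Section 7.3 plans, for each proportion indicator, that "the proportion of patients who receive the procedure, in the defined time window, among those eligible will be calculated". It gives no censoring rule and no time-to-event method.

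Section 5 says that the data for the primary objective relate only to 2017, which conflicts with section 3.

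**The concern.** The numerator can be reached only by someone observed for more than 6 months after the first dose. The denominator takes in everyone who received immunotherapy, whenever they started. A patient diagnosed in 2017, given another drug first and started on immunotherapy in the first half of 2018 is therefore scored as not continuing, even if still on treatment at cut-off. Lack of observation is counted as failure to continue.

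Measuring the KPIs is the primary objective, the protocol states a special focus on immunotherapy, and 11b is the only indicator of how long immunotherapy lasts. The confidence interval would not reflect the error, and more patients would not remove it. If sites differ in how often they use immunotherapy after another line, their values may differ even when persistence is the same.

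**Working it through.** The protocol states no expected value for KPI 11b and no number of immunotherapy patients (only about 400 patients overall, section 7.2), so there is no planned figure to reproduce. The check is calendar arithmetic plus a range.

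**Last observable start.** The latest first-dose date d must satisfy d + 6 months + 1 day ≤ 30 June 2018.
- 29 December 2017 + 6 months = 29 June 2018, plus 1 day = 30 June 2018: just observable.
- 30 December 2017 + 6 months = 30 June 2018: more than 6 months cannot be seen.

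So every first dose from 30 December 2017 to 30 June 2018 is a forced non-continuer.

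**Assumptions for the share affected** (none is given in the protocol):
- Index dates are uniform over 2017, one per day, numbered 1 to 365.
- The first anti-cancer drug is given at day 45 after index and must fall in 2017, as section 3 requires. This keeps index days 1 to 320 (320 + 45 = 365).
- All patients share one lag g from index to first immunotherapy.
- True continuation p beyond 6 months is the same in early and late starters.

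On this day count, 30 December 2017 is day 364 and 30 June 2018 is day 365 + 181 = 546. A start is in the data if index + g ≤ 546 and is late if index + g ≥ 364. The late share is L = late / observed starters, and the expected reported value is p × (1 − L), shown for an assumed p = 40%.

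| Lag g (days) | Observed starters | Late starters | L | Reported KPI |
|---|---|---|---|---|
| 45 (immunotherapy is the first drug) | 320 | 320 − 319 + 1 = 2 | 0.6% | 39.8% |
| 120 | 320 | 320 − 244 + 1 = 77 | 24.1% | 30.4% |
| 180 | 320 | 320 − 184 + 1 = 137 | 42.8% | 22.9% |
| 270 | 276 (546 − 270) | 276 − 94 + 1 = 183 | 66.3% | 13.5% |

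**Mixture.** If half the patients have g = 45 and half g = 180, L = (2 + 137) / (320 + 320) = 21.7% and a true 40% reads 0.40 × 0.783 = 31.3%. A site using immunotherapy only as first drug would read 39.8% with the same persistence.

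**Sensitivity to the entry rule.** Sections 4.1 and 4.3 do not repeat the requirement of a drug in 2017. Without it, all 365 index days stay in and L is 47/365 = 13%, 122/365 = 33%, 182/365 = 50% and 183/276 = 66% at the same four lags.

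**Sensitivity to the data window.** If section 5 governed (2017 data only), the last observable start would be 30 June 2017. Even with no delay from index to immunotherapy, 184/365 = 50% of starters would be unobservable.

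**The case against.** The strongest reply is that the cut-off falls six months after the 2017 treatment window closes, so almost everyone who starts immunotherapy in 2017 has the required calendar follow-up. The summary also describes immunotherapy as the first choice in many advanced cases. This stands: where immunotherapy is the first drug, the bias is negligible (0.6% late). A reader might infer that the KPI is seriously wrong for immunotherapy patients in general. The documents do not support that, because section 3 keeps out of the cohort anyone whose first drug comes in 2018.

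A reader might also infer that later-line immunotherapy in this cohort falls mostly in 2018, or that sites with equal persistence will necessarily show different values. The protocol gives neither the delay to immunotherapy nor the line mix by site. In the model above, starts in 2018 make up 75/320 = 23% at 120 days, 135/320 = 42% at 180 days and 181/276 = 66% at 270 days, so the first inference depends wholly on the lag. The second holds only if the sites differ in line mix or diagnosis dates.

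It can be said that 11b is one sub-item among 16 potential indicators in a descriptive study, in a table still marked as a draft, and that the analysis could add a restriction. That limits the reach of the point but does not answer it: the protocol fixes the numerator, denominator and cut-off, and an analysis that follows them reproduces the error. Nor does the word eligible in section 7.3 help, since the KPI table itself says who is in the denominator.

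**Conclusion.** The point holds with a limited scope. As written, KPI 11b is biased downward because first doses from 30 December 2017 to 30 June 2018 are counted as not continuing whatever happens. The bias sits almost wholly in patients who start immunotherapy in 2018 after another drug. Under the stated assumptions it takes a true 40% to about 40%, 30%, 23% or 13.5% at lags of 45, 120, 180 or 270 days. Each figure gives all patients one lag, so a real mix of first-line and later-line patients would lie between them. Distortion between sites is possible but not shown. Patients who die or stop within 6 months after a start on or before 29 December 2017 are true non-continuers and are not part of the problem.

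**What to change.** Add one sentence to the KPI 11b row, choosing one of two forms.

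1. Restrict the denominator to patients with more than 6 months of potential follow-up before the data cut-off: first immunotherapy dose on or before 29 December 2017 under section 3. Keep those who die or stop within 6 months as non-continuers. State whether the numerator needs a recorded dose after month 6. If it does, the limit must be earlier by one dosing interval; for illustration, administrations 14 or 21 days apart (an assumption) would move it to 15 or 8 December 2017.
2. Report the 6-month Kaplan-Meier probability of remaining on immunotherapy, with death or stopping as the event and censoring at cut-off for those still on treatment. This keeps the late starters, but needs a rule for reading the stopping date from administrative records.

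In either case, reconcile sections 3 and 5 on the data window, because the start limit and the censoring date depend on it.

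No new data are needed beyond what section 3 already collects. The first form has a smaller denominator and a wider interval, and under-represents later-line starters; the second adds one estimate and one definition.

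### KPI 13 divides 30-day drug starts by all MDT patients, so treatment choice and unretrievable trial therapy can be read as waiting time

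*Protocol*

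**What the plan says.** Protocol section 5.2 defines KPI 13 by its two counts. The numerator is "Number of patients who underwent first systematic anti-cancer drug administration within 30 days from MDT" and the denominator is "Total number of patients patients identified by the algorithm discussed in MDT meeting". Nothing limits the denominator to patients who had, or were planned for, systemic treatment.

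Section 7.3 gives the general rule for all indicators: "the proportion of patients who receive the procedure, in the defined time window, among those eligible will be calculated".

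Rows 10 and 11 of the same table carry a data limit: "For patients enrolled in experimental clinical trial will not be possible to retrieve information on therapies from administrative database". Row 5 has a related note: "The algorithm will not be able to identify patients who received neoadjuvant therapy in clinical trials". Rows 12 and 13 rely on the same drug records but carry no such note. KPI 12 divides by "Total number of patients identified by the algorithm who deceased".

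The cohort is described in two ways. Section 3 requires that patients "received at least one anti-cancer drug treatment between January 2017 and December 2017". Sections 4.1 (algorithm), 4.3 (inclusion criteria) and 7.1 (analysis population) contain no such requirement.

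**The concern.** A timeliness proportion should have in its denominator the patients for whom the clock is meaningful. An MDT meeting also discusses patients who go on to surgery, radiotherapy or supportive care alone. If they never receive a systemic drug, KPI 13 records them in the same way as patients who waited too long. A trial participant who started promptly but whose drug is not in the administrative data is recorded in that way too.

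The primary objective concerns appropriateness and quality of care among the participating sites, so a comparison between sites is the natural use of the figure. A site that treats more MDT patients without systemic drugs, or enrols more in trials, would look slower with the same waiting times. KPI 12 shares only the trial-data part. There, missing records lower the apparent use of drugs near death, which may make a site look better.

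**Working it through.** The protocol gives no expected value for KPI 12 or KPI 13 and no sample size calculation, so there is no stated figure to reproduce. The check has three parts.

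**1. Which patients are in the denominator under each cohort description**

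| MDT patient | Sections 4.1, 4.3, 7.1 | Section 3 |
|---|---|---|
| Never receives a systemic drug | in, counts as not in time | out |
| Drug only in a trial, no record | in, counts as not in time | out, as no treatment is visible in the data |
| First drug in a trial, a later drug recorded | in, may be dated too late | in if a recorded drug falls in 2017, may be dated too late |
| Drug given after surgery or radiotherapy, beyond 30 days | in, counts as late | in if the drug falls in 2017, counts as late |

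Section 3 therefore removes the first two groups and leaves the last two. The KPI 11a denominator, "Total number of patients identified by the algorithm who underwent anti-cancer drug treatment for NSCLC", would need no such restriction if every patient in the cohort were drug-treated. This suggests that the unrestricted cohort was in mind, but it does not settle the matter.

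**2. Direction and scale for KPI 13 under the unrestricted cohort**

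Let p be the true share starting within 30 days among drug candidates, u the share of MDT patients who are not candidates, and t the share of candidates with no retrievable drug because of a trial (assumed to have the same p). Then

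measured KPI 13 = p × (1 − u) × (1 − t).

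Both factors are at most 1, so the reading cannot exceed p. None of p, u and t is in the protocol. The values below are assumptions, with p = 70%.

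| | t = 0 | t = 5% | t = 10% | t = 20% |
|---|---|---|---|---|
| u = 0 | 70% | 66.5% | 63% | 56% |
| u = 20% | 56% | 53.2% | 50.4% | 44.8% |
| u = 40% | 42% | 39.9% | 37.8% | 33.6% |

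Two sites with the same p = 70% and t = 0, but u = 20% and u = 40%, would report 0.70 × 0.80 = 56% and 0.70 × 0.60 = 42%. That is a gap of 14 points with no difference in timeliness.

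For comparison, the 95% half-width at n = 400 (the expected total in section 7.2) and p = 70% is 1.96 × √(0.70 × 0.30 / 400) = 4.5 points. The real denominator is at most 400 overall and smaller per site, so sampling error will be larger than this. The bias does not shrink with n.

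With the denominator restricted to patients with a recorded first drug on or after the MDT date, the ratio is p(1 − u)(1 − t) / [(1 − u)(1 − t)] = p. This holds only if the excluded patients have no recorded drug at all. The last two groups in the first table are not corrected by it.

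**3. KPI 12**

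Only the trial-data term applies: measured KPI 12 = p × (1 − t), where t is now the share of decedents whose drugs are unretrievable. With an assumed p = 20%, the reading is 19%, 18% or 16% at t = 5%, 10% or 20%, a shift of 1 to 4 points. The 95% half-width at p = 20% is 1.96 × √(0.20 × 0.80 / 400) = 3.9 points even if all 400 patients had died, and wider with fewer deaths.

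**The case against.** The strongest counter-argument is section 3. If the cohort is drug-treated in 2017, patients managed without drugs and trial-only patients are not in the study, and most of the distortion goes. This stands as a condition on the point. It does not remove it, because sections 4.1, 4.3 and 7.1 omit the criterion and two of the groups above remain in either case.

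Second, the eligibility phrase in section 7.3 is generic, and each row's denominator can be read as supplying the eligible set. KPI 8 also divides by all MDT patients. This stands too: there is no textual contradiction with section 7.3. The difficulty is what the KPI 13 ratio measures. KPI 1 is the nearest comparison, since it is also a within-so-many-days indicator and divides only by patients who had the procedure. KPI 11a is a weaker comparison because it describes treatment mix.

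Third, the retrieval limit is already disclosed in rows 10 and 11, in the latter under a general heading on therapies. For rows 12 and 13 this is a matter of carrying a known caveat forward.

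Fourth, a treated-only denominator has faults of its own. It conditions on later treatment, drops patients who deteriorated or died while waiting, and still counts those who start a drug after surgery as late. This stands, and it is why the treated-only figure should sit beside the all-MDT figure and not replace it.

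A reader might also infer two stronger claims. One is that no surgical patient or trial participant can ever be a KPI 13 event. That is not so: KPI 13 does not exclude neoadjuvant patients, who may start a drug within 30 days, and a trial participant may have a recorded non-trial first drug in the window. The other is that the KPI 12 denominator breaks the eligibility rule. All deceased patients are a coherent set for drug use in the last 30 days of life, and KPI 14 uses the same set.

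**Conclusion.** The point holds for KPI 13, with limits. Under the cohort of sections 4.1, 4.3 and 7.1, the indicator combines how often MDT patients are given a systemic drug, how many are treated in trials, and how soon treatment starts. A difference between sites in the first two can appear as a difference in the third. Under section 3 much of this disappears, but not all, and the documents do not say which cohort governs.

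The direction under the unrestricted cohort follows from the definitions. The size does not, because the protocol gives neither the share of non-candidates nor the share of trial participants. Under the assumed values, the KPI 13 shift is 14 points or more once a fifth of MDT patients are not drug candidates (true value 70%). It comes mainly from non-candidates when trial participation is small.

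For KPI 12, what remains is a missing caveat. Its effect under the assumed values is 1 to 4 points, about the size of sampling error or less.

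**What to change.** 1. Reconcile section 3 with sections 4.1, 4.3 and 7.1, so that it is clear whether drug treatment in 2017 is a condition for entering the cohort.
2. Report KPI 13 among MDT patients with a first recorded systemic drug on or after the MDT date. Place it beside the all-MDT version and the share of MDT patients with no recorded drug. Show separately the patients who had major surgery between the MDT meeting and the first drug.
3. State in rows 12 and 13 that trial participants' drugs are not retrievable, so that the all-decedent KPI 12 and the all-MDT KPI 13 are read as lower bounds in that respect.

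The cost is a change of wording and a filter on data already being collected. Trial participants need not be identified in the anonymised records. The downside is that the treated-only version leaves out patients who were eligible but never treated, including those who died while waiting. The all-MDT version and the separate share keep them visible. A patient whose first drug was given in a trial and whose later drug is recorded will still be dated too late, and the caveat in row 13 should say so.
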